6.6.4. Visit Windows

All assessments will be summarized using analysis windows.

The terminology of unscheduled will be applied to assessments that are outside an analysis window regardless, of the nominal label associated with the assessments in the EDC system.

The following visit windows will be used in the summary of clinical data.

Table 3: Analysis Visit Windows

Nominal Period/Visit	Start (days)	Stop (days)
Baseline	1	1
Week 2 (Day 15)	2	21
Week 4 (Day 29)	22	35
Week 6 (Day 43)	36	49
Week 8 (Day 57)	50	63
Week 10 (Day 71)	64	77
Week 12 (Day 85)	78	91
Week 16 (Day 112)	92	120

Safety Endpoints

The following windows summarize the definition of treatment-emergent.

Table 4: Analysis Windows for Safety Endpoints

Window	Start	Stop
Adverse events	Sign of ICF	30 days post last dose
Treatment-emergent Adverse events, ECGs and Labs	Post first dose	Last dose + 30 days
Prior Medications	Prior to first dose	First dose
Concomitant Medications	Post first dose	Last dose + 24 hours
Post Medications	Post last dose + 24 hours	NA

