## 1.2 Schema

### 1.3 Schedule of Activities

	Screening Period	Treatment Period								Follow-up/ET
		1  Screening	2 Baseline	3	4	5	6	7	8	
VISIT NUMBER		0	2	4	6	8	10	12	16	
STUDY WEEK										
STUDY DAY 	12 weeks before Day 1	1	15	29	43	57	71	85		Last dose +30 days
Site Visits 	X	X		X		X		X	X	
Home Visits 			X		X		X			
Informed consent	X									
Inclusion/exclusion criteria	X	X								
Demography 	X									
Medical history 	X									
Prior medications 	X									
Concomitant medications 	X	X	X	X	X	X	X	X	X	

 For subjects rolling over from Study SPR001-201, the final safety follow-up visit of Study SPR001-201 may coincide with the screening visit of this study (with any overlapping assessments conducted only once). If a subject completed the final follow-up visit of Study SPR001-201 ≤3 months before the screening period of this study, overlapping assessments conducted at that final follow-up visit need not be repeated at screening for this study. If a subject completed the final follow-up visit of Study SPR001-201 >3 months before the screening period of this study, all screening assessments must be conducted anew, including some additional screening assessments specified for such subjects.

 All visits should be performed on the indicated study days. In cases where this is not possible, the following visit windows apply: ±3 days for Visits 3 to 8 and ±7 days for the safety follow-up visit (Visit 9). All visits, including the early termination visit, should be scheduled for the morning, to accommodate 8am laboratory assessments.

 Study visits for screening; at Weeks 0, 4, 8, and 12; and at final follow-up must be conducted as in-clinic outpatient visits.

 Study visits at Weeks 2, 6, and 10 may be conducted as either in-clinic outpatient visits or in-home visits by qualified study personnel.

 Demographic information needs to be collected only for SPR001-naïve subjects.

 Full medical history and prior medications from the past year will be collected for SPR001-naïve subjects. If a subject completed the final follow-up visit in Study SPR001-201 before the screening period for this study, any significant medical history and medications taken during the intervening period should be captured.

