### 7.2 Study Drug Discontinuation

Subjects may voluntarily discontinue study drug or the Investigator may discontinue a subject's study drug at any time. Investigators should discuss any safety concerns with the Medical Monitor as soon as possible to determine whether a subject should continue or discontinue study drug. Study drug will be discontinued in subjects who experience clinically significant liver chemistry, QTcF, or other individual treatment stopping criteria described in this section. Subjects may discontinue study drug but remain in the study for follow-up.

[figure not shown]
If study drug is discontinued, the Investigator will report the discontinuation to the Medical Monitor, document the date and reason for study drug discontinuation on the appropriate electronic case report form (eCRF), schedule an early termination visit for the subject (see the Schedule of Activities in [Section 1.3](#)), provide or arrange for appropriate follow-up, and document the course of the subject's condition.

Subjects who prematurely discontinue study drug may be replaced at the discretion of the Sponsor to ensure adequate numbers of evaluable subjects.

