## 12.2 Appendix of Liver Safety

### 12.2.1 Liver Chemistry Stopping Criteria and Follow-up Assessments

Liver Chemistry Stopping Criteria	
Absolute ALT	ALT $\geq$ 5x ULN
Increase in ALT	ALT $\geq$ 3x ULN persists for $\geq$ 4 weeks
Bilirubin	ALT $\geq$ 3x ULN and bilirubin $\geq$ 2x ULN (>35% direct bilirubin)
INR^2	ALT $\geq$ 3x ULN and INR $>1.5$ , if INR measured
Cannot Monitor	ALT $\geq$ 3x ULN and cannot be monitored weekly for 4 weeks
Symptomatic	ALT $\geq$ 3x ULN associated with symptoms (new or worsening) believed to be related to liver injury or hypersensitivity
Suggested Actions and Follow-up Assessments	
Actions	

• Immediately discontinue study drug.

• Report the event to the Sponsor or designated CRO within 24 hours.

• Complete the liver event eCRF, and complete an SAE data collection tool if the event also met the criteria for an SAE.

• Request list of any medications taken in last 48 hours; specifically question about medications that are known to increase liver enzymes, such as aspirin, acetaminophen, ibuprofen, naproxen, diclofenac, phenylbutazone, and any antibiotic use.

• Perform liver chemistry follow-up assessments.

• Monitor the participant until liver chemistry test abnormalities resolve, stabilize, or return to baseline (see MONITORING below).

• If restart/rechallenge is not granted, permanently discontinue study drug and continue participant in the study for any protocol-specified follow-up assessments.

	

• Viral hepatitis serology.

• Obtain INR and recheck with each liver chemistry assessment until the transaminase values show downward trend.

• Obtain blood sample for PK analysis after the most recent dose.

• Serum CPK and LDH.

• Fractionate bilirubin, if total bilirubin <math>\geq</math>2x ULN.

• Obtain complete blood count with differential to assess eosinophilia.

• Record the appearance or worsening of clinical symptoms of liver injury, or hypersensitivity, on the AE report form.

• Record use of concomitant medications (including acetaminophen, herbal remedies, and other over-the-counter medications) on the concomitant medications eCRF.

• Record alcohol use on the liver event eCRF.

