4. STUDY DESIGN

4.1. Summary of Study Design

[figure not shown]
This is a Phase 2 study of SPR001 for the treatment of classic CAH that will provide 12 weeks of open-label treatment to eligible subjects. To be eligible for this study, an individual must either have completed Study SPR001-201 or meet criteria for SPR001-naïve subjects outlined under Eligibility Criteria.

Subjects who enroll in this study will be treated with SPR001 at 400 mg once a day (QD) during the treatment period.

Study visits will occur every 2 weeks and should be scheduled for the morning, to accommodate 8 am laboratory assessments. Study visits for screening and at Day 1 (Baseline), Week 4, Week 8, and Week 12 (end of treatment) will be conducted as in-clinic visits. Study visits at Week 2, Week 6, and Week 10 may be conducted as either in-clinic visits or in-home visits by qualified study personnel. A final safety follow-up outpatient clinic visit will occur 30 days after the last dose of study drug.

To reduce subject burden, the final safety follow-up visit in Study SPR001-201 for subjects completing that study and rolling over into this study may coincide with the screening visit of this study (with any overlapping assessments conducted only once). Subjects who completed the final follow-up visit in Study SPR001-201 >3 months before screening in this study and subjects naïve to SPR001 must complete anew all specified screening assessments for this study. Subjects will maintain a stable dose and regimen of glucocorticoids throughout this study.

Figure 1: Study Schema

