6. CONSIDERATIONS FOR DATA ANALYSES AND HANDLING

All data from scheduled and unscheduled visits will be presented in the subject listings.

However, unless noted otherwise, only data from scheduled/windowed visits will be included in the summaries, statistical analysis, and calculation of derived parameters.

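### SAP Table 3 assigns visits by days from first dose only, so an early stopper's follow-up hormone sample (last dose + 30 days) can be summarised as Week 4 to Week 12

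*SAP*

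**What the plan says.** **Visit assignment.** SAP 6.6.4: "All assessments will be summarized using analysis windows". Table 3 gives Week 2 as Day 2-21, Week 4 as 22-35, Week 6 as 36-49, Week 8 as 50-63, Week 10 as 64-77, Week 12 as 78-91 and Week 16 as 92-120. Study day is counted from first dose (SAP 6.6.1). Last dose plays no part in Table 3. The same section applies the term unscheduled to "assessments that are outside an analysis window regardless, of the nominal label associated with the assessments in the EDC system". SAP 6 adds that, unless noted otherwise, "only data from scheduled/windowed visits will be included in the summaries, statistical analysis, and calculation of derived parameters".

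**Follow-up visit.** SAP 4.1: "A final safety follow-up outpatient clinic visit will occur 30 days after the last dose of study drug". Footnote 2 of the schedule, in both documents, allows 7 days either side. The key hormones row is marked at this visit. Protocol 4.2 describes these 30 days as a post-treatment washout that also serves to look for rebound of the HPA axis.

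**Early stoppers.** Protocol 7.2: "Subjects may discontinue study drug but remain in the study for follow-up". The same section tells the investigator to "schedule an early termination visit for the subject". For liver events where restart is not granted, Protocol 12.2.1 says to "permanently discontinue study drug and continue participant in the study for any protocol-specified follow-up assessments". The schedule has one combined column for follow-up and early termination.

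**Uses of the Week 12 value.** SAP 9.2 states the hormone hypothesis as baseline against Week 12. SAP 6.6.3 defines a hormone control responder by Week 12 ACTH and A4. SAP 6.7.1 leaves continuous endpoints unimputed, adds an LOCF sensitivity analysis for hormones, and counts a missing binary endpoint as a failure.

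**The concern.** Two clocks are in use. Treatment visits and Table 3 run from first dose; the follow-up visit runs from last dose. They agree for a subject who completes, or nearly completes, 12 weeks. For a subject who stops well before that, a sample at last dose + 30 days falls on a study day that Table 3 calls a treatment week.

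If that happens, a washout value is reported beside on-drug values, possibly at Week 12, which SAP 4.1 describes as end of treatment. It also drops out of the Week 16 row, the only place where follow-up data are summarised and where the rebound question would be read. With 11 subjects in all (SAP 4.3), and 17-OHP, ACTH and A4 tabulated only by subgroup (SAP 9.5 and 11.3), one record can move a visit mean.

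**Working it through.** **1. Where the follow-up sample lands.** Let L be the study day of last dose, 1 to 84. The nominal follow-up day is L + 30, looked up in Table 3.

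| Last dose (L) | L + 30 | Table 3 row | Number of L days |
|---|---|---|---|
| 1-5 | 31-35 | Week 4 | 5 |
| 6-19 | 36-49 | Week 6 | 14 |
| 20-33 | 50-63 | Week 8 | 14 |
| 34-47 | 64-77 | Week 10 | 14 |
| 48-61 | 78-91 | Week 12 | 14 |
| 62-84 | 92-114 | Week 16 | 23 |

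So Weeks 4-10 take 5 + 14 + 14 + 14 = 47 last-dose days, Week 12 takes 14 and Week 16 takes 23. These are counts of days, not probabilities.

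**2. With the 7-day tolerance.** The visit falls between L + 23 and L + 37.
- Week 12 can be reached if L + 37 ≥ 78 and L + 23 ≤ 91, so L = 41-68 (28 days).
- Every permitted day lies in the Week 16 row only if L + 23 ≥ 92 and L + 37 ≤ 120, so L = 69-83 (15 days).

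**3. Do other rules prevent it?**
- *Closest record (SAP 6.6.5).* The earliest permitted follow-up is L + 23. A sample taken no later than L + 7 is at least 23 - 7 = 16 days earlier. Each window from Week 4 to Week 12 is 14 days long, so two records in it are at most 13 days apart. No near-dose record shares the window, so none can displace the follow-up sample.
- *Table 4.* It uses last dose, but to define treatment-emergent events, ECGs and labs and to class medications. It assigns no visit week. Table 2 lists biomarkers apart from laboratory data, so Table 4 does not clearly cover hormones.
- *Per-protocol set (SAP 6.4.4).* Compliance is measured from first to last dose, so stopping early does not by itself exclude a subject. Efficacy uses the safety set by default (SAP 9.1).

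**4. Is the sample off drug?** Protocol 4.2 equates 32 to 44 days with about 5 to 7 times the terminal phase: 32/5 = 6.4 and 44/7 = 6.3 days. Read as half-lives (an assumption), the fraction left at 30 days is 0.5^(30/6.4) = 0.039 or 0.5^(30/6.3) = 0.037, about 4%.

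**5. What one record could do (illustration).** Assume an on-drug geometric mean ratio of 0.50 and one of n subjects back at baseline (ratio 1.0). The reported ratio is 0.5^((n-1)/n):
- n = 11: 0.533
- n = 5: 0.574
- n = 3: 0.630

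With n = 5, a half-way return on the log scale gives 0.5^0.9 = 0.536. Rebound to 1.5 times baseline gives 0.5^0.8 × 1.5^0.2 = 0.623. Subgroup sizes are not stated; 5 and 3 are assumed.

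**6. LOCF.** A follow-up value placed in Weeks 4-10 can be carried to Week 12. SAP 11.3 lists LOCF tables for 17-OHP, ACTH and A4, in the non-dexamethasone severe/moderate subgroup only.

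**The case against.** The strongest reply is that the triggering visit is not clearly required. Protocol 7.2 asks for an early termination visit and only permits further follow-up, Protocol 12.2.1 concerns liver events, and SAP 5.1.4 lets the final analysis proceed once subjects reach Week 16 or discontinue before it. An early termination visit made promptly, with no later return, lands in roughly the right week. This stands: the problem needs an early last dose and an attended hormone draw near + 30 days. A reader might infer that every early stopper is misplaced, or that the reported Week 12 result is biased. The documents support neither, since they give no count of early stoppers or of their follow-up draws.

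Second, a sample on Day 85 is at Week 12 from first dose, and including all data regardless of stopping is a legitimate analysis. A reader might infer that the SAP meant an on-treatment analysis and that Table 3 breaks it. That goes too far, because neither intention is stated. What remains is that the rule as written mixes washout samples into treatment weeks without saying so, while Protocol 4.2 gives the same sample a different purpose.

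Third, the sentence about EDC labels concerns records outside a window. That an in-window follow-up record is reassigned follows from the rule that all assessments use the windows, not from that sentence.

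Fourth, consequences are limited. Hormones are secondary, p-values are nominal (SAP 9.1), the study is hypothesis-generating (SAP 9.4) and all values stay in the listings. The ratios above rest on assumed inputs. This limits the weight of the point but does not remove the gap.

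**Conclusion.** The point holds as a conditional defect in the visit-window rule. If a subject stops early and attends the follow-up visit, Table 3 places the washout hormone sample in Weeks 4-10 for a last dose on Day 1-47 and in Week 12 for Day 48-61 (Day 41-68 possible with the tolerance). It can then enter the baseline-to-Week 12 comparison, the responder definition and LOCF. No other rule in the SAP stops this, and no passage says it is intended.

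The day arithmetic is certain; the effect on results is not, and may be zero. A shift towards no effect is plausible if hormones return to baseline off drug, but no figure from this study shows it. The responder consequence is also limited: SAP 11.3 lists no responder table. The rule should be corrected because the change is cheap and the assignment ought not to depend on who happens to stop early.

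**What to change.** In SAP 6.6.4:

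1. For the on-treatment hormone summary, admit to Weeks 2-12 only samples taken within a stated lag after last dose, for example 7 days. That keeps a Week 12 visit at the end of its permitted range (Day 88) for any last dose from Day 81 (88 - 81 = 7). The lag is a choice to be stated, because drug is still present then: on the half-life reading above, 0.5^(7/6.4) = 0.47.
2. Key the follow-up row to last dose. Make it wider than the 7-day visit tolerance, so that it holds all samples after the lag, and show days since last dose. A late Week 12 visit (last dose Day 83, sample Day 91, so + 8) then moves to this row and is not lost.
3. Also show the Week 12 hormone summary with all data regardless of stopping, labelled as such, and state which of the two is the main summary.
4. State whether LOCF carries on-treatment values only or all values. On-treatment-only carry-forward credits stoppers with on-drug suppression at Week 12, which favours the drug. Note too that a stopper left without a Week 12 value counts as a responder failure under SAP 6.7.1.

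Cost: SAP wording, a last-dose condition in the window derivation, a relabelled row and one extra Week 12 hormone summary; no new data. The downside is fewer values and possible selection of completers in the on-treatment summary, which the all-data summary beside it offsets.

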6.6.5. Multiple Assessments

In general, if multiple, valid, non-missing observations exist at a visit or collection time point then records will be chosen based on the following rules.

The record closest to the nominal time point in question.

If 2 records are equidistant: later record if the two visits.

If 2 records with same date/time: average (generally applies to assessments done in triplicate).

6.7. Handling of Missing Data

6.7.1. Missing Efficacy Endpoints

Missing data will not be imputed for continuous efficacy endpoints in primary or secondary analyses.

A sensitivity analysis will impute missing hormone data using last observation carried forward.

For binary efficacy endpoints, missing data will be assumed as a failure (subject did not meet the efficacy endpoint).

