 Subjects should be on a stable regimen of glucocorticoid replacement for a minimum of 12 weeks before baseline and throughout the treatment period. On the mornings of all study visits, including screening, subjects should hold off on taking any morning glucocorticoid medication until after laboratory assessments have been completed. On all other days during the study, subjects may take any morning dose of glucocorticoid medication at their usual time.

	Screening Period	Treatment Period								Follow-up/ET
		2 Baseline	3	4	5	6	7	8	9	
VISIT NUMBER	1 Screening									
STUDY WEEK		0	2	4	6	8	10	12	16	
STUDY DAY	12 weeks before Day 1	1	15	29	43	57	71	85		Last dose +30 days
Site Visits	X	X		X		X		X	X	
Home Visits			X		X		X			
Clinical laboratory 	X	X	X	X	X	X	X	X	X	
HbA1c and fasting insulin 		X		X		X		X		
Key hormones 	X	X	X	X	X	X	X	X	X	
Exploratory adrenal hormones 		X		X		X		X		
PK 	X	X		X		X		X	X	
Hepatitis B & C and HIV screening 	X									
eGFR for screening 	X									
Pregnancy test for WOCP 	X	X		X		X		X	X	
Vital signs  and body weight	X	X	X	X	X	X	X	X	X	
Physical examination 	X	X		X		X		X	X	

 Samples for these lab assessments will be obtained at the beginning of each study visit (8am), after overnight fast (nothing to eat since the previous midnight), and before the subject has taken any morning dose of glucocorticoid medication. If a morning dose of study drug is added, samples for these lab assessments will be obtained before the morning dose of study drug for that day (where applicable).

 Clinical laboratory assessments include hematology, clinical chemistry, fasting glucose, lipid panel, thyroid panel, urinalysis, LH, FSH, inhibin B, SHBG, renin, aldosterone, and, for females only, estradiol, prolactin, and progesterone.

 ACTH, 17-OHP, androstenedione, testosterone, and background glucocorticoid levels (cortisol/prednisolone/dexamethasone, depending on what the subject is taking) will be measured from blood samples. 17-OHP will also be measured from a saliva sample.

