The schedule of study visits every 2 weeks during the treatment period and the option for some study visits to be in-home visits provides an appropriate balance between closely monitoring subject safety / response to therapy and minimizing subject burden. The 30-day post-treatment washout period in this study allows for adequate safety follow-up and analysis of any HPA axis rebound after the last dose of study drug.

Subjects will take study drug with a meal or after consumption of a standardized snack in order to improve absorption of study drug, since the Phase 1 clinical studies showed minimal study drug absorption when subjects were dosed in a fasted state. Specific dose reduction criteria, strict individual treatment stopping criteria, and appropriate laboratory and medical assessments have been established to ensure subject safety.

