9.5.1. Efficacy Analysis of Hormones

Hormones [17-OHP; ACTH; A4; Testosterone] will be summarized using geometric means and geometric means ratios to assess change and percentage change.

A summary of [17-OHP; ACTH; A4; Testosterone] by Visit will include the observed parameter (using GM reporting format).

Figures

A serial figure with week as the x-axis and % change as the y-axis will be provided.

Separate serial figures will be provided for each hormone.

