11.3. Tables, Figures and Listings

This index may be updated post finalization of the SAP.

Tables

Number	Title	Analysis Set
14.1.1.1.1	Enrollment by Investigator	Randomized
14.1.1.3	Analysis Sets	Randomized
14.1.1.4	Subject Disposition	Randomized
14.1.1.5.1	Summary of Protocol Deviation Identified Prior To Database Lock by Site	Randomized
14.1.1.5.2	Summary of Protocol Deviation Identified Prior To Database Lock by Treatment Group	Randomized
14.1.1.6	I/E Table	Randomized
14.1.2.1.1	Demographic and Baseline Characteristics	Safety
14.1.2.2.1	Summary of Baseline Hormones	Safety
14.1.2.3.1	Mini International Neuropsychiatric Interview	Safety
14.1.3.1	Medical History by System Organ Class and Preferred Term	Safety
14.1.3.2	Prior Medications	Safety
14.1.3.3	Prior Glucocorticoid Therapy	Safety
14.2.1.1	Summary of 17-OHP by Visit: Dexamethasone Subjects	Safety
14.2.1.2	Summary of 17-OHP by Visit: Non-Dexamethasone Severe/moderate Control Issues	Safety
14.2.1.3	Summary of 17-OHP by Visit: Non-Dexamethasone Severe/moderate Control Issues- LOCF	Safety
14.2.1.4	Summary of 17-OHP by Visit: Non-Dexamethasone Mild Control Issues	Safety
14.2.2.1	Summary of ACTH by Visit: Dexamethasone Subjects	Safety
14.2.2.2	Summary of ACTH by Visit: Non-Dexamethasone Severe/moderate Control Issues	Safety
14.2.2.3	Summary of ACTH by Visit: Non-Dexamethasone Severe/moderate Control Issues- LOCF	Safety
14.2.2.4	Summary of ACTH by Visit: Non-Dexamethasone Mild Control Issues	Safety
14.2.3.1	Summary of Androstenedione by Visit: Dexamethasone Subjects	Safety
14.2.3.2	Summary of Androstenedione by Visit: Non-Dexamethasone Severe/moderate Control Issues	Safety
14.2.3.3	Summary of Androstenedione by Visit: Non-Dexamethasone Severe/moderate Control Issues- LOCF	Safety
14.2.3.4	Summary of Androstenedione by Visit: Non-Dexamethasone Mild Control Issues	Safety
14.2.4.1	Summary of Testosterone by Visit	Safety
14.2.4.2	Summary of Testosterone by Visit: Males	Safety
14.2.4.3	Summary of Testosterone by Visit: Females	Safety
14.2.5	Summary of SF-36 by Visit	Safety
14.2.6	Summary of CAH Signs and Symptoms	Safety
14.2.7	Summary of Patient Global Impression of Change	Safety
14.2.8	Changes in Lipid Profile Summary by Visit	Safety

Number	Title	Analysis Set
14.2.9	Changes in Insulin Profile Summary by Visit	Safety
14.2.10	Changes in Body weight Summary by Visit	Safety
14.2.11	Summary of the Magnitude of Bothersome Symptoms	Safety
14.3.1.1	Study Drug Exposure	Safety
14.3.1.2	Study Drug Compliance	Safety

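### The LOCF rule for hormones has no visit limit, so the LOCF sensitivity outputs can show an on-drug value at the off-drug Week 16 visit; and no planned output estimates Week 16 against Week 12

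*SAP*

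**What the plan says.** **Missing hormone data.** SAP 6.7.1 has two relevant sentences. The first governs the main analyses: "Missing data will not be imputed for continuous efficacy endpoints in primary or secondary analyses". The second adds the sensitivity analysis: "A sensitivity analysis will impute missing hormone data using last observation carried forward". Neither limits the visits to be filled, and neither separates on-treatment from post-treatment values.

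**Where LOCF appears.** SAP 11.3 lists three LOCF tables (14.2.1.3, 14.2.2.3, 14.2.3.3) with matching serial figures, for 17-OHP, ACTH and A4. One is titled "Summary of ACTH by Visit: Non-Dexamethasone Severe/moderate Control Issues- LOCF". All are for the same subgroup, and each has an unimputed counterpart (14.2.1.2, 14.2.2.2, 14.2.3.2). Testosterone has no LOCF output.

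**Week 16.** SAP 4.1: "A final safety follow-up outpatient clinic visit will occur 30 days after the last dose of study drug". Both schedules of activities mark key hormones at that visit. SAP Table 3 gives it an analysis window of Days 92 to 120, counted from first dose. Under SAP 6.6.4, a value outside every window is relabelled unscheduled. Under SAP section 6, unscheduled values stay out of summaries and derived parameters unless otherwise noted.

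**Purpose of the washout.** Protocol 4.2 says the 30 days allow for safety follow-up and for "analysis of any HPA axis rebound after the last dose of study drug".

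**Planned estimates.** SAP 9.5.1 says the hormones "will be summarized using geometric means and geometric means ratios to assess change and percentage change". The reporting format in SAP 11.1 names baseline as the only reference for percentage change, and SAP Table 2 sets baseline at Day 1 before dosing. The hypothesis in SAP 9.2 compares baseline with Week 12.

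**The concern.** LOCF within a treatment period assumes that the last value still describes the subject under the same conditions. That assumption fails across the end of dosing. If the drug lowers these hormones, the last on-drug value is low and the off-drug value should be higher. Carrying the first into the place of the second makes suppression appear to persist after washout.

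In a single-arm study, the return of hormones after stopping is useful within-subject evidence that the fall was due to the drug. A rule that shrinks this return in any output, together with the absence of an estimate of it elsewhere, leaves a purpose named in the protocol without a clean analysis.

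**Working it through.** The plan gives no figure to reproduce. The check has four parts.

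**1. Is Week 16 off drug?** Protocol 4.2 equates 32 to 44 days with about 5 to 7 times the terminal phase. Taking that phase as a half-life (an assumption), 32/5 = 6.4 days and 44/7 = 6.3 days. Thirty days is then 30/6.4 = 4.7 to 30/6.3 = 4.8 half-lives, and 0.5 to those powers leaves about 4% of the drug. Week 16 is effectively an off-drug visit.

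**2. Can a permitted follow-up miss the window?** Inputs: Week 12 is Day 85 ± 3 and follow-up is last dose + 30 ± 7 days (schedules of activities). I take the last dose as the evening before the Week 12 visit (Day 84) or the day of it (Day 85).

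| Last dose | Nominal follow-up | With ± 7 | With Week 12 ± 3 as well |
|---|---|---|---|
| Day 84 | 114 | 107 to 121 | 104 to 124 |
| Day 85 | 115 | 108 to 122 | 105 to 125 |

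The analysis window closes at Day 120. A permitted visit on Days 121 to 125 becomes unscheduled and leaves the summaries. LOCF would then insert the Week 12 value although a real off-drug value exists. So a missed visit is not the only trigger.

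The mirror image also arises. After an early stop with the last dose on Days 48 to 61, the 30-day off-drug sample falls on Days 78 to 91, which is the Week 12 window.

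**3. Effect on the Week 16/Day 1 ratio.** Suppose k of n subjects are imputed with a carried ratio c and all others are truly back at baseline (ratio 1). The displayed geometric mean ratio is c^(k/n). With c = 0.30 and k = 1:

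- n = 5: 0.30^(1/5) = 0.79, an apparent 21% residual suppression where the other four show none.
- n = 4: 0.30^(1/4) = 0.74, an apparent 26%.

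**4. Effect on the Week 16/Week 12 ratio.** If the true off-drug/on-drug ratio is R in every subject and k of n are filled from Week 12, the displayed ratio is R^(1 − k/n). With n = 5:

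| R | k = 0 | k = 1 | k = 2 |
|---|---|---|---|
| 1.5 | 1.50 | 1.38 | 1.28 |
| 2 | 2.00 | 1.74 | 1.52 |
| 3 | 3.00 | 2.41 | 1.93 |

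The values of c, R, k and n are all assumed. The documents give only the final total of 11 subjects (SAP 4.3). The LOCF tables cover one subgroup of those, so a small n is plausible but not stated.

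**The case against.** The strongest reply is that very little rests on the LOCF outputs, and much of it stands.

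- **The main analyses are untouched.** A reader might infer that the trial's evidence on rebound is blurred. The documents do not support that. SAP 6.7.1 rules out imputation in the main hormone analyses, so those tables and figures use observed values. Each LOCF table has an unimputed counterpart that would reveal any artefact.
- **The harm is conditional.** It needs a missing or out-of-window Week 16 value and an LOCF output that displays Week 16. The SAP does not say that it does, and since its hypothesis ends at Week 12 a programmer might stop there. But nothing tells the programmer to, and by-visit outputs with Week 16 among the visits point the other way.
- **On and off drug can be compared informally.** A reader might infer that no output sets the two side by side. By-visit tables and serial figures would show Weeks 12 and 16 together. What is missing is a direct paired estimate with an interval.
- **Rebound is not an endpoint.** The protocol says the washout allows such analysis but lists no such objective. If rebound means overshoot above the pre-treatment level, Week 16/Day 1 is the relevant ratio and is already planned. This is a reason to report both ratios.
- **The distortion is small against the noise.** With an assumed within-subject log SD of 0.3 to 0.7, a change has SD √2 times that, 0.42 to 0.99. At n = 5 (t = 2.776) the 95% interval multiplies and divides the ratio by exp(2.776 × SD/√5), about 1.7 to 3.4. A shift from 1.00 to 0.79 lies inside that. But it is a bias in a known direction that one sentence removes.
- **Stopping LOCF at Week 12 is not a full cure.** For a subject who stops early, a filled Week 12 value is still a last on-treatment value. That is true, and the outputs should say so.

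**Conclusion.** The point holds in a limited form. Followed as written, the LOCF rule can place an on-drug value at a visit about 30 days off drug, including for subjects who attended within the permitted window. If the hormones had fallen on drug, this understates their return. It affects sensitivity outputs for three hormones in one subgroup and nothing else. The illustration of 0.79 (n=5) or 0.74 (n=4) in place of 1.00 rests on one imputed subject, a carried ratio of 0.30 and full return in the others. It shows scale and is not a prediction. It should not be extended to all 11 subjects, because no LOCF table for all subjects is planned.

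The second part holds as a gap: the protocol gives rebound as a use of the washout, and the SAP leaves the Week 12 to Week 16 change to be judged by eye.

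Severity is low to moderate. SAP 9.4 calls the study hypothesis-generating, p-values are nominal, and the primary objective is safety.

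**What to change.** 1. In SAP 6.7.1, state that LOCF carries on-treatment values only, fills visits only through Week 12, and is never applied to Week 16. Footnote the LOCF outputs to say that a filled visit after early discontinuation shows the last on-treatment value.
2. Report Week 16 as observed. Define its analysis window by days since last dose (30 ± 7, that is 23 to 37 days), which also keeps early stoppers' off-drug samples out of the Week 12 window. At the least, extend Table 3 from Day 120 to Day 125.
3. Add a descriptive output: the paired Week 16/Week 12 geometric mean ratio with 95% CI for each hormone, from observed data, in subjects dosed to Week 12. Show it in the planned subgroups and overall, alongside Week 16/Day 1. The overall row needs a stated exception to SAP 9.5, which confines hormone analysis to subgroups.

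The cost is a few sentences and one row per hormone per table, with no new data. The downside is small: a few more unadjusted estimates, restricted to subjects who completed dosing and imprecise at this sample size.
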